5.7.2.4. Sensitivity Analysis of Key Secondary Endpoint Variables

In order to assess the robustness of more clinically relevant between group comparisons for the analysis of the key secondary efficacy endpoint, the same statistical analysis method approach as described above in Sec 5.7.2 will be applied in the mITT population. The intent-to-treat estimand will be replaced by the on-treatment estimand, which is defined as all key secondary efficacy endpoints values collected during the efficacy treatment period (Sec 3.1.2).

5.7.2.5. Summary of Results by Time Point

Central laboratory values (in conventional (US) and international units), percent change from baseline, and/or when appropriate absolute change from baseline (in conventional and international units) will be summarized at protocol scheduled visits by treatment group for calculated LDL-C, Total-C, fasting TG, non-HDL-C, Apo B, Apo CIII, Lp(a), Apo-A1, and ratio Apo-B/Apo-A1. Summaries will include both the ITT and mITT populations. Further details are described below:

- For lipids other than TG and Lp(a): LS mean and SE for each treatment group, obtained from the same MMRM models as used for endpoints above and including planned time points (see Section 5.7.2.1) and with raw values, changes from baseline, and percent change from baseline as response variable in the model as appropriate.
- For lipids other than TG and Lp(a): Observed data raw values, change from baseline (as applicable), and percent change from baseline response variables will be summarized by patient counts, mean and SD for each treatment group at all planned time points.

- For TG and Lp(a): mean and SE for each treatment group obtained from multiple imputation approach followed by the robust regression models as used for endpoints above and including planned time points (see Section 5.7.2.2) and with raw values or percent changes from baseline as response variable in the model as appropriate.
- For TG and Lp(a): Observed data raw values and percent change from baseline response variables will be summarized by patient counts, mean and SD for each treatment group at all planned time points.

During the OLTP, efficacy variables will be explored through descriptive statistics at each protocol scheduled visit for the total patients administered open-label study treatment (total), as well as by the patient subgroups of study treatment received in the double-blind treatment period (i.e., evinacumab, placebo). Formal statistical testing is not planned. Descriptive statistics will include the observed values of the same parameters as described for each variable in the DBTP, for patients in the open-label safety analysis set.

For patients receiving evinacumab in the DBTP, a combined summary including both the DBTP and OLTP assessments may be considered, referencing the double-blind baseline for variable calculations. Prolonged time between last dose of double-blind treatment and first dose of open-label treatment will need to be taken into consideration when combining longitudinal efficacy data. Formal statistical testing is not planned. Descriptive statistics will include the observed values of the same parameters as described for each variable in the DBTP, for patients in the double-blind safety analysis set.

Adjustment for Multiple Comparison

In order to handle multiple key secondary endpoints during the DBTP for the comparison of the evinacumab group and the placebo group, the overall type-I error will be controlled by the use of a hierarchical inferential approach. Statistical significance of the primary parameter at the 0.05 alpha level is required before drawing inferential conclusions about first key secondary parameter. Inferential conclusions about successive key secondary parameters require statistical significance of the prior one. The hierarchy testing sequence is the order of endpoints as presented in Sections 4.7.1 and 4.7.2.

This fixed hierarchical approach will ensure a strong control of the overall type-I error rate at the 0.05 level.

No further adjustments will be made for other secondary endpoints for which p-values will be provided for descriptive purpose only.

No adjustment will be made for the first step and second-step statistical analyses (Section 7), since the primary and key secondary endpoints testing will have been concluded at the time of the first step analysis.

5.8. Analysis of Safety Data

The summary of safety results will be presented separately for the DBTP and OLTP, unless otherwise noted. Safety summaries for the DBTP will be presented by treatment groups (evinacumab, placebo) containing patients from the double-blind safety analysis set. Safety summaries for the OLTP will be presented by all patients and by treatment group in DBTP (i.e.,

evinacumab, placebo), for patients in the open-label safety analysis set. No formal inferential testing will be performed for either period. Summaries will be descriptive in nature.

General common rules

All safety analyses will be performed, unless otherwise specified, using the following common rules:

- Safety data in patients who do not belong to the safety analysis set (i.e., exposed but not randomized) will be listed separately.
- PCSV values are defined as abnormal values considered medically important by the Sponsor according to predefined criteria/thresholds based on literature review and defined by the Sponsor for clinical laboratory tests and vital signs (PCSV version dated January 2009 [Appendix 10.4]). Considering that the threshold defined in the PCSV list for monocytes and basophils can be below the ULN, the following PCSV criterion will be used for the PCSV analysis of monocytes and basophils:
 - PCSV criterion for monocytes: >0.7 Giga/L or $>ULN$ (if $ULN \geq 0.7$ Giga/L).
 - PCSV criterion for basophils: >0.1 Giga/L or $>ULN$ (if $ULN \geq 0.1$ Giga/L).
- PCSV criteria will determine which patients had at least 1 PCSV during the respective TEAE periods, taking into account all evaluations including unscheduled or repeated evaluations.
- The treatment-emergent PCSV denominator by treatment group for a given parameter will be based on the number of patients assessed for that given parameter at least once during the respective TEAE periods.
- All measurements, scheduled or unscheduled, fasting or not fasting, will be assigned to Global Analysis Windows defined in Appendix 10.2 /Table 1 in order to provide an assessment for the screening visit through follow-up visit time points.
- For quantitative safety parameters including central laboratory measurements and vital sign scores, descriptive statistics will be used to summarize observed values and change from baseline values by visit.
- Analyses performed according to diabetes status will be done considering diabetic patients as patients with either type 1 or type 2 diabetes in the medical history e-CRF page (regardless of the ongoing status).

5.8.1. Adverse Events

In general, the primary focus of AE reporting will be on TEAEs summarized in respective TEAE periods, specifically the DBTP and OLTP. Post-treatment AEs will be summarized separately.

If an AE onset date (occurrence, worsening, or becoming serious) is incomplete, an imputation algorithm will be used to classify the AE as pre-treatment, treatment-emergent, or post-treatment. The algorithm for imputing date of onset will be conservative and will classify an AE as treatment-emergent unless there is definitive information to determine pre-treatment or

post-treatment status. Details on classification of AEs with missing or partial onset dates are provided in Section 6.3.

Adverse event incidence tables will present the number (n) and percentage (%) of patients experiencing an AE by SOC and PT. In addition, incidence tables by SOC, HLGT, HLT, and PT will be provided for all TEAEs, serious TEAEs, and TEAEs leading to permanent treatment discontinuation. Multiple occurrences of the same event in the same patient will be counted only once in the tables within a treatment phase (TEAE or post-treatment AE). For tables presenting severity of events, the worst severity will be chosen for patients with multiple instances of the same event. The denominator for computation of percentages is the respective safety analysis set within each treatment group.

AE incidence tables will present data by SOC sorted alphabetically and PT sorted by decreasing frequency of the evinacumab treated group, and summarize the number (n) and percentage (%) of patients experiencing an AE.

Analysis of all treatment-emergent adverse events

The following TEAE summaries will be generated:

- Overview of TEAEs, summarizing number (%) of patients with any
 - TEAE;
 - Serious TEAE;
 - TEAE leading to death;
 - TEAE leading to permanent treatment discontinuation.
- All TEAEs by primary SOC, HLGT, HLT, and PT
- All TEAEs by primary SOC and PT
- Number (%) of patients experiencing common TEAE(s) presented by primary SOC and PT (PT incidence $\geq 5\%$ in any treatment group)
- All TEAEs relationship (related/not related) to evinacumab
- All TEAEs by maximum severity (i.e., mild, moderate or severe)
- A common TEAE related to any clinically significant signal will be further characterized as appropriate. The characterization of the clinically significant signal can include Kaplan-Meier curves for time from first dose to first occurrence of selected TEAE, time to resolution, and event duration. Patients without any event will be censored at the end of the respective TEAE period.

Analysis of all treatment emergent serious adverse event(s)

- All Serious TEAEs by primary SOC, HLGT, HLT, and PT
- All Serious TEAEs by primary SOC and PT
- Patient listings of serious TEAEs will be provided in the report appendix.

- All Serious TEAEs relationship (related/not related) to evinacumab
- A serious TEAE related to any clinically significant signal will be further characterized as appropriate. The characterization of the clinically significant signal can include Kaplan-Meier curves for time from first dose to first occurrence of selected TEAE, time to resolution, and event duration. Patients without any event will be censored at the end of the respective TEAE period.

Analysis of all treatment-emergent adverse event(s) leading to treatment discontinuation

- All TEAEs leading to permanent treatment discontinuation, by primary SOC, HLG, HLT, and PT
- All TEAEs leading to permanent treatment discontinuation, by primary SOC and PT
- Patient listings of TEAEs leading to permanent treatment discontinuation will be provided in the report appendix.
- A TEAE leading to permanent treatment discontinuation and related to any clinically significant signal will be further characterized as appropriate. The characterization of the clinically significant signal can include Kaplan-Meier curves for time from first dose to first occurrence of selected TEAE, time to resolution, and event duration. Patients without any event will be censored at the end of the respective TEAE period.

Post-treatment adverse events

- All post-treatment AEs by primary SOC and PT
- All post-treatment SAEs by primary SOC and PT

Analysis of Cardiovascular events

- TEAEs suspected of being CV events by primary SOC and PT
- TEAEs suspected of being CV events categorized by adjudicated outcome of positive, negative, or in-process (as applicable)
- Number of patients with adjudication positive by outcome categories, specifically CHD death, non-fatal MI, fatal and non-fatal ischemic stroke, unstable angina requiring hospitalization, congestive heart failure requiring hospitalization, ischemia driven coronary revascularization procedure
- Patient listing of positively adjudicated TEAE CV events

Analysis of all treatment-emergent adverse event(s) by status of negative mutation in both LDLR alleles (Yes, No) – receptor-negative/negative vs not receptor-negative/negative

- All TEAEs by primary SOC and PT
- All Serious TEAEs by primary SOC and PT
- All TEAEs leading to permanent treatment discontinuation, by primary SOC and PT
- All TEAEs leading to death by primary SOC and PT

Patient Deaths

The following summaries of deaths will be generated.

- Number (%) of patients who died by study period (TEAE and post-treatment) and reason for death;
- TEAEs leading to death (death as an outcome on the AE CRF page, as reported by the Investigator) by SOC and PT.

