7. STUDY TREATMENTS

7.1. Investigational and Reference Treatments

Evinacumab or placebo IV infusion.

In the DBTP, eligible patients will be enrolled to receive an IV dose of evinacumab 15 mg/kg Q4W or matching placebo, starting on day 1. The last dose of double-blind study drug will be at week 20.

In the open-label portion of the study, patients will receive

- Evinacumab at 15 mg/kg IV Q4W starting at week 24 (day 169) with the last dose at week 44 (day 309)

Dosing should fall within a window of ± 7 days; if >14 days has passed, skip the dose and return to the original schedule.

Instructions on dose preparation and administration are provided in the pharmacy manual.

Instructions on management of infusion reactions are provided in Section 7.5.1.

Sterile alirocumab drug product will be supplied at a concentration of 150 mg/mL in a prefilled pen for patients from study R727-CL-1628 who enroll in this study.

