3.3. Open-Label Safety Analysis Set

The open-label SAF considered for safety analyses will be the randomized population who received at least 1 dose or part of a dose of open-label study drug.

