4.8.1. Adverse Events Variables

The period of safety observation starts from the time when the patient gives informed consent and continues into the following periods:

- The PRE-TREATMENT period is defined from the day the ICF is signed to the day before the first dose of double-blind study treatment administration.
- The double-blind treatment-emergent adverse event (TEAE) period is defined from the day of the first dose of double-blind study treatment administration to the day of the last dose of double-blind study treatment administration + 168 days (24 weeks) for those patients not proceeding into the OLTP, or up to the day before the first dose of open-label study treatment administration for those patients proceeding into the OLTP

The double-blind TEAE period will include:

- The TREATMENT period is defined from the day of first double-blind study treatment administration up to the day of last double-blind study treatment administration + 35 days. For patients entering into the OLTP, the treatment period will be truncated at the day before the first dose of open-label study treatment administration.
- The RESIDUAL TREATMENT period is defined from the day of last double-blind study treatment administration + 36 days up to the day of last double-blind study treatment administration + 168 days (24 weeks), or up to the day before first dose of open label study treatment administration, whichever is earlier.
- The open-label treatment-emergent adverse event (TEAE) period is defined from the day of the first open-label study treatment administration to the day of the last open-label study treatment administration + 168 days (24 weeks). For patients entering the open-label study R1500-CL-1719, the TEAE period will be truncated at the day before first study treatment administration in R1500-CL-1719.

The open-label TEAE period will include:

- The TREATMENT period is defined from the day of first open-label study treatment administration up to the day of last open-label study treatment administration + 35 days.
- The RESIDUAL TREATMENT period is defined from the day of last open-label study treatment administration + 36 days up to the day of last open-label study treatment administration + 168 days (24 weeks).

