7. TIMING OF STATISTICAL ANALYSES

Efficacy and safety analyses for this study will be performed in two steps, specifically for patient data collected up to the time the last patient completes efficacy assessments at week 24 (step 1 consisting of the DBTP) and at the end of the study (step 2 for the OLTP). No formal interim analysis for efficacy is planned since analyses of primary and key secondary efficacy endpoints will be final at the time of first step analysis. Therefore, no multiplicity adjustment for multiple analyses is needed (see Section 5.7.2.5). The timing for patient data to be reported is defined below for each step:

- First step: efficacy analyses up to week 24 and interim safety analysis
 - This analysis will be conducted on all randomized patients when all patients will have all their lipid data up to week 24 efficacy analysis window collected and validated.
 - The efficacy analyses will be performed up to week 24 visit. Analyses of endpoints up to week 24 visit will correspond to the final analyses for these endpoints. Analysis of lipid parameters beyond week 24 visit will be descriptive.
 - The safety analyses will be performed on all safety data (double-blind and open-label) collected up to the common cut-off date. For this analysis, the common cut-off date is defined as date of the last week 24 visit.
- Second-step: final analysis
 - This analysis will be conducted at the end of the study and will consist of the final analysis of efficacy data at time points beyond the week 24 visit and final safety analysis.

Individuals involved in the first step analysis of the study will not be involved in the conduct of the study afterwards; individual patient identification will not be released to anyone who is directly involved in the conduct of the study. The first step analysis process, the measures used to protect the blind and the integrity of the study, the communication plan, and the confidentiality agreement will be described in a separate document. The results of the first analysis will not be used to change the conduct of the ongoing study in any aspect.

Analyses methods and conventions described in the other sections of this SAP will be applied for all analyses as applicable. The following additional rules will apply for analyses performed at first step analysis:

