- Any lipid assessments within efficacy analysis windows up to the week 24 visit will be taken into account (may include few unscheduled lipid data soon after the cut-off date).
- Patients without end of treatment visit performed at the time of the cut-off date will be considered as ongoing and exposed up to the cut-off date. Therefore:
 - Patients who did not complete the respective treatment period nor prematurely discontinued the study treatment at cut-off date will be analyzed as “ongoing” in the disposition summary.
 - Their TEAE period and treatment period will end at the cut-off date.
 - Their treatment duration will be derived by considering date of cut-off as last administration date.
- Analyses of number of administrations, and mean administration frequency will be performed up to the last administration reported in the e-CRF up to the cut-off date.
- AEs occurring, worsening or becoming serious after the cut-off date will not be included in the analyses. However, any available outcome before database lock, regardless of timing in relation to the cut-off date, of an adverse event starting prior to the cut-off date will be taken into account. Medications, treatment discontinuations/completions and deaths occurring after the cut-off date will not be included in the analyses.
- Post-treatment period, and post-study period are not applicable for ongoing patients. Analyses of post-treatment AEs, post-study deaths and post-treatment medications will be performed for patients who either completed or prematurely discontinued the treatment before or at the cut-off date.
- Analysis of status at last study contact and proportion of patients with insufficient follow-up will be provided for patients who either completed or prematurely discontinued the treatment before or at the cut-off date.

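### Open-label adverse event tables give crude percentages over unequal follow-up, so the figures depend on accrual timing and extension uptake as well as on the drug

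*SAP*

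**What the plan says.** The denominator counts patients, not time: "The denominator for computation of percentages is the respective safety analysis set within each treatment group" (SAP 5.8.1). The open-label set is "the randomized population who received at least 1 dose or part of a dose of open-label study drug" (SAP 3.3), so one partial infusion makes a patient a full unit of the denominator.

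Events count from the first open-label dose until 168 days after the last (SAP 4.8.1), with one exception: "For patients entering the open-label study R1500-CL-1719, the TEAE period will be truncated at the day before first study treatment administration in R1500-CL-1719". Protocol 10.4.4.1 has no such truncation, and SAP 1.2.4 does not list it as a change.

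The first-step analysis includes open-label safety data. There, "the common cut-off date is defined as date of the last week 24 visit", and for patients still on treatment, "Their TEAE period and treatment period will end at the cut-off date" (SAP 7).

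Some time-aware summaries are planned. SAP 5.5 requires Kaplan-Meier plots of discontinuation due to adverse events in both periods. SAP 5.8.2 gives infusion reactions per administration and time to the first one. For other events, SAP 5.8.1 offers Kaplan-Meier curves only as an option once a clinically significant signal is being characterised. No other adverse event table has a person-time measure.

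**The concern.** A crude percentage can be read as a risk only when follow-up is roughly equal. In the double-blind period it nearly is, for patients who proceed to open-label treatment. In the open-label period, length of observation is set by when a patient was randomised relative to the last patient (first step) and by whether the patient enters the extension (final step).

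Protocol 10.4.9.1 says the first analysis may support a submission dossier, and that is when open-label follow-up can be shortest. A low open-label percentage could then be taken for good longer-term tolerability. A higher one at the final step could be taken for late toxicity. Either could arise with no change in the underlying rate.

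**Working it through.** **1. Length of the windows.** Protocol 7.1 puts the first open-label infusion at day 169 and the last at day 309.

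- Completer not entering the extension: 309 + 168 = day 477. This reproduces the end-of-study visit in the schedule (day 477, week 68). The window is 477 − 169 = 308 days = 44.0 weeks.
- Completer entering the extension, assuming a first dose there at the week 48 visit (day 337): days 169 to 336 = 168 days = 24.0 weeks.
- Double-blind period for a patient who proceeds: days 1 to 168 = 24.0 weeks.
- First step: the last patient's week 24 visit is both the cut-off date and the first open-label dosing day, so that patient contributes 1 day.

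**2. Do the exposure tables supply the time at risk?** SAP 4.6 defines open-label duration as last dose + 28 days − first dose. For any completer this is (309 + 28 − 169)/7 = 24.0 weeks, whether the event window was 24 or 44 weeks. Both fall in the top band of 20 weeks or more. The difference cannot be recovered from these tables.

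**3. Effect on the percentage.** Assumptions, none from the documents: constant hazard, uniform accrual over A weeks, all patients complete and receive open-label drug, and extension uptake u. With 24-week risk p, the weekly hazard is λ = −ln(1 − p)/24. For p = 0.10, λ = 0.10536/24 = 0.00439.

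First step, all completers entering the extension: crude risk = [24 − p/λ + (A − 24)p]/A.

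- A = 26: (24 − 22.78 + 0.20)/26 = 5.5%. Mean open-label time is (24²/2 + 2 × 24)/26 = 12.9 weeks.
- A = 52: (1.22 + 2.80)/52 = 7.7%.
- A = 78: (1.22 + 5.40)/78 = 8.5%.

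With no extension uptake the last two become 10.4% and 12.8%.

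Final step: crude risk = u·p + (1 − u)(1 − e^(−44λ)). Here 1 − e^(−0.1932) = 17.6%, so u = 1, 0.5 and 0 give 10.0%, 13.8% and 17.6%.

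| True 24-week risk | First step, A = 26 / 52 / 78 (u = 1) | Final step, u = 1 / 0.5 / 0 | Rate per 100 patient-years |
|---|---|---|---|
| 5% | 2.7 / 3.9 / 4.2% | 5.0 / 7.0 / 9.0% | 11.2 |
| 10% | 5.5 / 7.7 / 8.5% | 10.0 / 13.8 / 17.6% | 22.9 |
| 20% | 11.1 / 15.6 / 17.0% | 20.0 / 26.8 / 33.6% | 48.5 |
| 50% | 29.6 / 39.8 / 43.2% | 50.0 / 61.0 / 71.9% | 150.7 |

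Across these scenarios the crude figure for a 10% event spans 5.5% to 17.6%, about threefold, at one fixed rate. The 5% row also bears on the common-event table, which lists terms reaching 5% in any group: the same event is expected below that line at the first step and can be well above it at the final step.

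**The case against.** Several points on the other side stand.

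- The plan is not blind to time. Discontinuations due to adverse events have required Kaplan-Meier plots, and infusion reactions are scaled to administrations. Both are already partly covered.
- SAP 5.8 presents the two periods separately and descriptively, with no formal testing. It specifies no contrast between them, so misreading would be the reader's step. The percentages will still be read against each other, because open-label results are also split by double-blind arm.
- Open-label dosing duration, ongoing patients and extension entrants are all tabulated. A reader can see that first-step exposure is short, but cannot obtain time at risk over the 168-day window (step 2 of the working).
- Accrual length and uptake are assumed. The largest figures need no extension uptake and an unchanged hazard through days 345 to 477 (19 weeks), which SAP 4.8.1 classes as residual treatment.
- With 57 patients, the standard error at 20% is √(0.2 × 0.8/57) = 5.3 points. The 52- and 78-week first-step shifts (4.4 and 3.0 points) lie within it. The 26-week shift (8.9) and the no-uptake shift (13.6) do not. These are systematic shifts in the expected value, so sampling error does not excuse them.
- A patient-year rate assumes a constant hazard. If events cluster after early doses, off-drug follow-up dilutes it. This bears on the choice of measure and is met by offering a fixed-week estimate.

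**Conclusion.** The point holds as a cheap improvement. Crude open-label percentages mix the event rate with follow-up that depends on accrual and extension uptake. They are not comparable between the first-step and final analyses, or with the roughly 24-week double-blind percentages. Under the stated assumptions the distortion runs from about half the 24-week risk (5.5% against 10%) to about 1.8 times it (17.6% against 10%). The window lengths follow from the documents, apart from the assumed day of entry to the extension. The percentages do not.

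A reader might infer more than the documents support:

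- **That the percentage reflects follow-up instead of the drug.** It still rises with the true hazard; the two influences simply cannot be separated.
- **That every open-label table spans one day to 44 weeks.** The one-day end exists only at the first step. At the final step the spread for completers is about 24 to 44 weeks. A 44-week patient appears at the first step only if accrual lasts about that long.
- **That the randomised safety comparison is compromised.** It rests on the double-blind period and is unaffected.

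**What to change.** In SAP 5.8.1 and 5.8.2, for the open-label overview, serious event, special interest and common event tables at both steps:

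1. Keep n (%).
2. Show total patient-time at risk over the open-label event window.
3. Add one follow-up-adjusted measure: either patients with a first event per 100 patient-years (time to first event or end of window), or a Kaplan-Meier cumulative incidence at a stated week such as 24.
4. Give the double-blind evinacumab arm the same measure, and base any statement across periods or analysis steps on it.

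The R1500-CL-1719 truncation should also be listed in SAP 1.2.4.

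The cost is SAP wording and an extra column or two. Dose and onset dates are already collected. The patient-year rate brings a constant-rate assumption, which the fixed-week estimate avoids. The fixed-week estimate needs enough patients still at risk: with 26-week accrual only about 57 × 2/26 ≈ 4 patients would have reached 24 open-label weeks at the first step, so an earlier week or the patient-year rate would serve better there.

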9.4.6. Follow-up

Adverse event information will be collected until the patient's last study visit.

Serious adverse event information will be collected until the event is considered chronic and/or stable.

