2.2. Sample Size and Power Considerations

For the primary efficacy hypothesis during the DBTP, a total sample size of 57 patients (38 on evinacumab and 19 on placebo) will have 90% power based on a two sample t-test to detect a treatment group difference in mean percent change LDL-C of 38% with a 0.05 two-sided significance level and assuming a common standard deviation of 35% using nQuery 7.0. This

sample size has been adjusted for a 5% non-evaluable patient rate for the primary efficacy endpoint, and a 15% dropout rate.

To gain experience with evinacumab in the population of Japanese patients, this study will plan to enroll up to 9 patients in Japan. Due to the rare patient population planned for evaluation, the sample size of 9 patients (15% of the planned study sample size) was chosen for practical reasons, centered on the feasibility to identify and enroll these patients into the trial. Based on the Ministry of Health, Labor, and Welfare 2007 “Basic Principles on Global Clinical Trials” method 1, a sample size of 12 (21%) will be needed to achieve 80% probability that the effect in Japan is at least ½ of the global effect. A sample size of 9 provides approximately 77% probability.

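### The optional Kaplan-Meier curves for selected TEAEs keep event-free patients at risk after adverse-event observation has ended, which modestly understates risk

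*SAP*

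**What the plan says.** SAP 5.8.1 provides that characterising a clinically significant signal "can include Kaplan-Meier curves for time from first dose to first occurrence of selected TEAE". The same censoring sentence follows for common TEAEs, serious TEAEs and TEAEs leading to permanent discontinuation: "Patients without any event will be censored at the end of the respective TEAE period".

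SAP 4.8.1 fixes the end of the period. In the double-blind part it is "last dose of double-blind study treatment administration + 168 days (24 weeks) for those patients not proceeding into the OLTP". Patients who continue have a shorter period, which stops just ahead of their first open-label infusion. In the open-label part it is the last open-label dose plus 168 days, except that for patients entering the extension study "the TEAE period will be truncated at the day before first study treatment administration in R1500-CL-1719". SAP section 7 adds that, at the first-step analysis, the period of patients still ongoing ends at the cut-off date. It excludes adverse events starting after the cut-off for everyone. Neither section ends the period at the last visit, withdrawal or loss to follow-up.

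Protocol 9.4.6 says "Adverse event information will be collected until the" last study visit of the patient. Protocol 9.4.2 goes further for serious events. If a patient left the study early, an SAE with onset within 168 days of the last dose is still reported, provided the investigator learns of it.

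**The concern.** Kaplan-Meier estimation is useful here because it can remove patients from the risk set when they are no longer observed. The SAP rule removes an early leaver at a date set by dosing, not by observation. Between the last visit and that date no non-serious event can be recorded, yet the patient stays in the denominator as event-free. The estimate is pushed down, and further down in an arm that loses more patients. These curves would be drawn only when a safety signal needs a closer look, in groups planned at 38 and 19 patients.

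The first-step rule has a similar gap. A patient who has stopped treatment and had the end-of-treatment visit is not classed as ongoing, so the cut-off does not end that patient's TEAE period. If the last dose was less than 168 days before the cut-off, the patient is at risk on paper during time in which events are excluded by rule. This happens even if follow-up is complete.

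**Working it through.** **What the 15% is.** The documents give no figure for these curves. The only related number is the sample-size allowance "for the primary efficacy endpoint, and a 15% dropout rate" (SAP 2.2). The stated total reproduces. A two-sample t-test (difference 38, SD 35, two-sided 0.05) has 89.9% power with 14 + 28 patients and 91.9% with 15 + 30. Then 15/(0.95 × 0.85) = 18.6, rounded up to 19, and 19 + 38 = 57. So 15% is an efficacy allowance. It is borrowed below only as an assumed proportion leaving before safety follow-up is complete.

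**Dates.**
- Fully followed patient: last open-label dose day 309, end-of-study visit day 477; 477 − 309 = 168. There is no gap.
- Early leaver, for example with last dose on day 57 and last visit on day 62: censored on day 57 + 168 = 225, leaving 225 − 62 = 163 unobserved days counted as event-free.
- Patient dosed only on day 1: period ends on day 1 + 168 = 169. A completer's double-blind period ends the day before open-label dosing on day 169.

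Under the planned schedule no event-free patient leaves the double-blind risk set before week 24. The week-24 Kaplan-Meier estimate is therefore the crude proportion with a recorded event.

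**Expected week-24 estimate.** Let R be the true risk, w the proportion leaving, f the share of leavers still followed, and P the mean probability that a leaver's event occurs before leaving. Then:

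estimate = (1 − w)R + w[fR + (1 − f)P]

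Event times are taken as exponential: λ = −ln(1 − R)/168. With R = 0.20, λ = 0.22314/168 = 0.001328 per day.

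- Pattern A: last dose equally often on days 1, 29, 57, 85 and 113, leaving 5 days later. P = (0.008 + 0.044 + 0.079 + 0.113 + 0.145)/5 = 0.0778.
- Pattern B: leaving spread evenly over 168 days. P = 1 − 0.20/0.22314 = 0.1037.

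With w = 0.15:

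| Case | Calculation | Estimate |
|---|---|---|
| A, none followed | 0.85 × 0.20 + 0.15 × 0.0778 | 18.2% |
| B, none followed | 0.85 × 0.20 + 0.15 × 0.1037 | 18.6% |
| A, half followed | 0.925 × 0.20 + 0.075 × 0.0778 | 19.1% |
| Bound: all leave at once, none followed | 0.85 × 0.20 | 17.0% |

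A simulation under pattern B (38 patients, 5000 runs, no leaver followed) gave a mean estimate of 18.5% under the SAP rule and 19.9% with censoring at last contact.

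**Range.** Under pattern B with none followed, 5% to 20% leaving and true risks of 10% to 50%, the relative understatement is about 2% to 10%.

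**Unequal leaving.** With R = 0.20 in both arms, pattern B and none followed, 20% leaving gives 0.80 × 0.20 + 0.20 × 0.1037 = 18.1%. With 5% leaving it is 0.95 × 0.20 + 0.05 × 0.1037 = 19.5%. The difference is spurious.

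**First-step gap.** SAP section 7 sets the cut-off at the last week-24 visit. Nearly every patient is therefore past week 24 by then, and this gap bears mainly on the double-blind curve after week 24 and on the open-label curve. It is not in the figures above.

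**The case against.** The strongest reply is that the period matches planned follow-up. Protocol 6.3 and 8.1.5 ask for at least 24 weeks of follow-up after the last dose even for early leavers, and patients who stop drug in the double-blind period are to stay on the visit schedule. This stands as a reason to expect few unobserved days, and it makes the none-followed rows an extreme. It does not remove the gap. Patients may withdraw at any time. Protocol 10.4.1 counts patients last seen less than 23 weeks after the last infusion, and SAP section 7 plans to report insufficient follow-up.

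Second, serious events are partly captured through Protocol 9.4.2. That stands, and it leaves non-serious TEAEs as the main problem.

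Third, the curves are optional and descriptive, and under this rule they agree with the crude incidence tables that are the main AE report. At 38 patients and 20% risk the standard error is √(0.20 × 0.80/38) = 6.5 points, well above the bias. All of this stands and limits the severity.

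Fourth, not every early end of observation is missing information. A patient who has died, or has already stopped drug for another reason, cannot later have a first TEAE leading to discontinuation. Keeping that patient event-free gives the cumulative incidence. With assumed hazards equivalent to 10% for the event and 15% for other exits, the true incidence is 9.2%, against 10.0% if other exits are censored. This stands. A reader might infer that all three curves should be censored at death or last contact, but death and prior discontinuation are competing events.

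**Conclusion.** The point holds as a minor one. For withdrawal, loss to follow-up and the first-step cut-off, the stated rule counts unobserved or excluded time as event-free. It lowers the estimated risk, mainly for non-serious TEAEs and possibly unequally by arm. Under an assumed 15% leaving and a true 24-week risk of 20%, the shortfall is 1.4 to 1.8 points if no leaver is followed and about 0.9 points if half are. Event risks, leaving times and the share followed are assumptions; the documents give none.

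Two stronger readings are not supported. A reader might infer from SAP 2.2 that 15% of patients are expected to be lost to safety follow-up, but that figure belongs to the efficacy sample size. A reader might also infer that the main safety results or a formal comparison are distorted. SAP 5.8 plans no inferential safety testing, SAP 5.8.1 plans no person-time rates, and the main AE tables are crude proportions that do not use this censoring rule.

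**What to change.** In the common-TEAE and serious-TEAE bullets of SAP 5.8.1, censor patients without the event at the earliest of:

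- the end of the respective TEAE period;
- the last study visit or contact at which adverse events were ascertained (for the serious-event curve, a later documented contact that established SAE status counts);
- at the first step, the cut-off date, for all patients and not only those ongoing.

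Do not add censoring at death. Leave the curve for TEAEs leading to discontinuation out of the last-contact change.

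The cost is one sentence in two bullets. Visit and contact dates are already collected, fully followed patients are unaffected apart from the first-step cut-off, and estimated risks would rise slightly.
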